3.2 Study design and endpoints

3.2.1 Study design

The aim of this study is to investigate the effect of introducing daily and environmentally aware patient monitoring protocols outside hospitals and interventions informed by it, on all-cause and cardiovascular mortality, heart failure hospitalisations or emergency room visits, and quality of life in patients with symptomatic chronic heart failure (HF), patients with implanted Left Ventricular Assist Device (VAD) and heart transplant (HT) recipients.

Patient specific measures related to the vitals (including weight, blood pressure, heart rate, peripheral capillary oxygen saturation), daily physical activity, quality of sleep (as expressed through heart rate variability), psychological state and nutrition intake will be collected. In addition, the study will collect real world data derived from non-medical sources regarding environmental factors in the living environment of patients participating in the study (i.e., ambient temperature, relative humidity, pollutants).

The data will be collected through a Randomised Clinical Trial (RCT) where the aforementioned groups of patients, between 18 and 75 years of age, will be observed in an outpatient setting through the remote monitoring platform of RETENTION, which will be created for this purpose, and the standard clinical practice. A total of 450 participants will be recruited to participate in the study. 30-35% of the recruited patients will be women. This is because up until now, women have been underrepresented in most heart failure clinical trials, despite the fact that disease prevalence remains generally the same between both sexes. When it comes in heart failure with reduced ejection fraction, subgroup analysis of several trials reveals that women were older, more likely to have pre-existing hypertension and less likely to have coronary artery disease. In addition, despite heavier symptom burden, women fared better in survival and hospitalisation risk. LVAD implantation has also been studied mainly on male patients with the added restriction of smaller ventricular dimensions rendering device support unavailable in women.

A control group of patients of similar age dispersion will also be set up and followed up only by the standard means and procedures currently employed as best practices. This will be a multi-centre RCT conducted at six clinical centres in Greece, Italy, Germany and Spain.

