3.5 Statistical analysis plan and power calculation

The power analysis for the clinical study of RETENTION is based on a similar analysis performed for the TIM-HF-2 evaluating a telemonitoring intervention² with similar endpoints and considering similar inclusion criteria:

- Chronic heart failure New York Heart Association (NYHA) class II or III
- Echocardiographically determined left ventricular ejection fraction (LVEF) ≤45%
- Hospitalisation due to decompensated HF within the last 12months before randomisation
- Depression score PHQ-9<10

For the sample size calculation, TIM-HF-2 used data for specific subgroups from the TIM-HF trial for sample size calculations. For the patient subgroup that mirrored the population they did include in the TIM-HF-2 trial, 19 days were lost due to all-cause death or unplanned cardiovascular hospital admissions at 12 months

² Koehler F, Koehler K, Deckwart O et. al. Lancet. 2018 Sep 22;392(10152):1047-1057. doi: 10.1016/S0140-6736(18)31880-4. Epub 2018 Aug 25. PMID: 30153985.

in the usual care group, and 12 days were lost for patients in the remote patient management group, which corresponds to a 38% reduction. The estimated standard deviation (pooled) was 48 and based on that they calculated that 750 patients would be required in each group to detect this difference with a power of 80% and a two-sided α of 5%.

For RETENTION we expect a slightly higher decrease in the endpoint (40%). If we apply the same rate of losses TIM-HF trial for control group(19 days per year) to a follow up period of 18 months, we expect a mean of 29 (19+10) days lost due to all-cause death or unplanned cardiovascular hospital admissions in the usual care group and 17 days lost in the test group (-40% of 29). Under these assumptions, the number of patients for each group of the study should be 199 (398 in total). Hence, accounting for about 10% of attrition rate and loss to follow up, the recruitment target for the study has been set to 450 patients.

Group sample sizes of 199 and 199 achieve 80% power to reject the null hypothesis of equal means difference with a standard deviation for both groups of 48 and with a significance level (alpha) of 0,05 using a one-sided test.

Statistical analysis plan

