- Demographic, clinical, and device data, and treatment results will be summarised using descriptive summary statistics. Data collected in the trial will be summarised overall and by treatment groups. Continuous variables will be presented with the numbers of observations, means, standard deviations, minimums, and maximums. For comparisons, the difference between the groups will be summarised with the difference of the two means together with 95% confidence intervals and tested using the two-sample t-test. These calculations will be done under the assumption that the data for the two groups are independent and approximately gaussian in distribution. If asymptotic assumptions fail, nonparametric summary statistics (medians, 25th and 75th percentiles) may be displayed. In addition, more appropriate non-parametric tests will be considered if the assumptions for the parametric tests are violated. For the comparison of two independent samples, if the data are not normally distributed, Mann-Whitney rank sum test will be performed instead of the parametric t-test,
- For categorical variables results will be summarised with subject counts, percentages. The differences between the two treatment groups will be summarised with the difference in percent and compared using the chi-square test or Fisher's exact test as appropriate.
- Survival analysis techniques will be used to analyse the time-to-event variables.

The primary analyses will compare the days lost due to unplanned cardiovascular hospitalisations or all-cause death and the survival free from death or unplanned hospitalisation/ambulatory administration of intravenous therapy between interventions group and usual care group by the means of the parametric t-test or non-parametric rank sum test as mentioned above.

To evaluate the additional measure of the primary outcome, the survival free from the combined endpoint, survival curves will be constructed using Kaplan-Meier estimates. Log-rank test results will also be computed for comparison of survival distributions between intervention and usual care groups.

Pre-specified subgroup analyses include:

- The three patient categories (HF, LVAD and HT)
- Males and Females
- Patients with a hospitalisation less than three months from the enrolment

• Patients older than 60 years

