- Cardiac Resynchronisation Therapy, with defibrillator (CRT-D) or without defibrillator (CRT-P)
- Aortic Aneurysm
- Heart Transplant
- LVAD Implant
- HF & CV medical therapies (ACEI/ARNI/ARB, BB, MRA, SGLT2i, diuretic, anticoagulant, antiplatelet, statin, amiodarone

Non-cardiovascular history

- Smoker [never, current, past (meaning >6 months)]
- Severe alcohol intake [never, current, past (meaning >6 months)]
- Thyroid disease (if yes, define hyper- or hypo-thyroidism)
- Cancer
- Anaemia
- Chronic Obstructive Pulmonary Disease (COPD)
- Chronic Kidney Disease
- Benign Prostatic hyperplasia
- Other than HF & CV medical therapies
- Recent HF hospitalisation discharge date, or recent urgent ED visit due to HF date
- Number of HF hospitalisations within the last 12 months
- Caregiver data (if caregiver available):
- Sex
- Date of birth, age
- Children (yes/no)
- Living situation (Living alone /Living with the person that cares for only /Living with the person cared for and other family members/ Other)
- Highest level of education (Up to and including high school/ Above high school education/ Other)
- Employment status (Working (full or part time) /Not currently working / Full-time homemaker / Retired /Student or other)
- Caregiver condition (Cardiovascular Disease/ Hypertension/Diabetes mellitus/ High cholesterol)

Data collected at every clinic visit (upon registration and at months 4,8,12 and 18):

- Weight
- Vital signs: Blood pressure, heart rate, Peripheral capillary oxygen saturation, Temperature
- ECG
- Rhythm
- Heart rate
- Conduction delay(LBBB,RBBB, LAH, LPH, incomplete RBBB or LBBB)
- QRS duration
- QTc
- PQ/PR
- Blood tests at months 4,8,12 (Urea, Creatinine, Potassium, Sodium, SGOT, SGPT, LDH, INR, CPK, Troponin, Uric Acid, CRP, White blood cells, Haemoglobin, Platelets and NT-proBNP)
- Blood tests at months 0(registration) and 18(Urea, Creatinine, Potassium, Sodium, SGOT, SGPT, LDH, INR, CPK, Troponin, Uric Acid, CRP, White blood cells, Haemoglobin, Platelets and NT-proBNP, Glucose, Magnesium, Cholesterol, Triglycerides, HDL, LDL, γGT, ALP, Total proteins, Albumin, Total Bilirubin, D-Dimers, Fibrinogen, Calcium, Phosphorus, CRP, Procalcitonin, TSH, FT3, FT4, B12, Fe, Ferritin)
- Depression score PHQ-9
- Kansas City Cardiomyopathy Questionnaire (KCCQ)
- Six-minute walk test
- Cardio-pulmonary exercise testing (upon registration and at month 18)

- VE/VCO2
- VO2max
- RER
- Echocardiography (upon registration and at months 8 and 18)

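### The primary comparison of days lost is valid but unadjusted, so it gives up precision that the stratification factors and baseline predictors already collected could provide at almost no cost

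*Protocol*

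**What the plan says.** Section 3.5 of the protocol names the test for days lost: the arms are compared "by the means of the parametric t-test or non-parametric rank sum test as mentioned above". The earlier bullet in that section says that, for non-normal data, the "Mann-Whitney rank sum test will be performed instead of the parametric t-test". No covariate, stratum or regression model is named for this comparison. Event-free survival gets Kaplan-Meier curves and a log-rank test, again with no covariates.

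Elsewhere the protocol supplies what an adjusted analysis would need:

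- Section 3.2.1 stratifies randomisation by centre and by patient type (HF, LVAD, transplant), in blocks of four. Sex, age, NT-proBNP and earlier admissions are not strata.
- Section 3.7.3 collects age, sex and NT-proBNP at registration, and also "Number of HF hospitalisations within the last 12 months".
- Section 3.2.1 remarks that "women fared better in survival and hospitalisation risk", in a discussion of heart failure with reduced ejection fraction, and sets the share of women at 30-35%.

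In section 3.5, patient category, sex, recent hospitalisation and age over 60 appear only as subgroup factors.

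**The concern.** Days lost combines death and unplanned cardiovascular admission. Patient type, age, natriuretic peptide level and recent admissions can all be expected to predict it. When they are left out, the variation they explain stays in the error term, and a chance imbalance in an unstratified factor is carried into the estimate without correction in that realised sample. For centre and patient type the problem differs slightly. Stratified blocks already limit imbalance, but a plain two-sample test gives no credit for it, so its standard error is too large.

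The design has little power to spare: 80% at 199 per arm, with recruitment raised to 450 only to cover about 10% attrition. Subgroup analyses do not help, because they do not adjust the overall comparison.

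**Working it through.** **Inputs, all from section 3.5.** "Group sample sizes of 199 and 199 achieve 80% power"; the test is run "with a significance level (alpha) of 0,05 using a one-sided test"; for usual care, "we expect a mean of 29 (19+10) days lost"; the test-arm mean is 17 days, so the difference is 29 - 17 = 12 days; the SD is 48 days in both arms.

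**Reproducing the plan's figure.** n per arm = 2 x (1.645 + 0.842)^2 x 48^2 / 12^2 = 197.8, so 198 by the normal approximation. The noncentral t calculation gives 199 (power 0.8008 at 199, 0.7991 at 198). The stated 199 is therefore an unadjusted, one-sided calculation, and it is correct as such.

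**Effect of adjustment.** Let R2 be the share of outcome variance explained by baseline variables. The protocol does not give it, so the values below are assumptions.

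- Residual SD = 48 x sqrt(1 - R2)
- SE = residual SD x sqrt(2/199)
- Power = Phi(12/SE - 1.645)
- Equivalent unadjusted sample = 398/(1 - R2)

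| Assumed R2 | Residual SD | SE (days) | Power | Equivalent total n | n per arm for 80% |
|---|---|---|---|---|---|
| 0 | 48.00 | 4.81 | 80.2% | 398 | 198 |
| 0.01 | 47.76 | 4.79 | 80.6% | 402 | 196 |
| 0.05 | 46.78 | 4.69 | 82.0% | 419 | 188 |
| 0.10 | 45.54 | 4.57 | 83.7% | 442 | 179 |
| 0.20 | 42.93 | 4.30 | 87.4% | 498 | 159 |

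**Sex alone.** R2 = p(1 - p)D^2/48^2, with p the share of women (0.30-0.35) and D an assumed difference between the sexes in mean days lost. D = 6, 10 and 20 days give R2 of about 0.003, 0.01 and 0.04, and power of 80.3%, 80.5% and about 81.5%.

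**Chance imbalance in sex.** With 32.5% women and 199 per arm, the SD of the arm difference in share of women is sqrt(0.325 x 0.675 x 2/199) = 0.047, so the 95% range is about +/-9 percentage points. At the edge of that range the unadjusted estimate moves by 0.9 day if D = 10 and 1.8 days if D = 20, against an SE of 4.81 and a target of 12.

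**Ignored strata.** Suppose centre and patient type alone explain 5%, 10% or 20% of the variance (assumed) and are balanced by design.

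- The t-test's actual one-sided error rate is 1 - Phi(1.645/sqrt(1 - R2)) = 0.046, 0.041 or 0.033, not 0.05. The test is conservative.
- Its power is Phi(0.849/sqrt(1 - R2)) = 80.8%, 81.5% or 82.9%, where 0.849 = 12/4.81 - 1.645. For any part of R2 that comes from the strata, the gain from adjustment is therefore somewhat smaller than the table shows.

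**The case against.** The strongest reply is that nothing here is an error. In a 1:1 randomised trial an unadjusted comparison is unbiased over randomisation, its standard error already allows for chance imbalance in unstratified factors, and the power calculation was made for this same unadjusted difference. This stands: the point is about efficiency, not validity. A reader might infer from the missing covariates that the planned result would be biased or the test invalid. The documents do not support that, and for the stratified factors the test errs on the cautious side.

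A reader might also infer that sex is the main omission, because the protocol itself calls it prognostic. That goes too far. The remark in section 3.2.1 concerns heart failure with reduced ejection fraction, whereas 250 of the 450 planned patients (section 3.4.1) are LVAD or transplant patients, for whom no outcome by sex is given. Sex alone adds about 1.5 power points at most over the range examined.

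The size of the gain rests wholly on an assumed R2. With means of 17 to 29 and an SD of 48 the outcome must be strongly skewed, and nothing in the protocol shows that a linear model would reach 20%. At 1% the gain is about 0.4 point. This stands too, and it is why the range starts near zero.

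The choice of covariates is often left to a separate SAP. Here, though, section 3.5 is itself headed as the analysis plan and fixes the test, so a later SAP that adjusted would depart from it.

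**Conclusion.** The point holds as a worthwhile, nearly free improvement. Section 3.5 fixes an unadjusted primary test while the trial records likely predictors and stratifies on two factors that the test ignores. At 199 per arm the one-sided power of 80% would become about 81%, 82%, 84% or 87% for an R2 of 1%, 5%, 10% or 20%. These figures assume the plan's 12-day difference and SD of 48, and that linear adjustment reduces the residual variance in proportion to R2. The true R2 cannot be derived from the document.

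A two-sided 5% test on the same inputs has 70% power. That shortfall comes from the choice of a one-sided test and should not be read as a consequence of omitting covariates.

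**What to change.** Before unmasking, replace the primary test in section 3.5 with a linear model for days lost. The primary estimate is the arm difference in means, with robust standard errors because the outcome is skewed. Covariates: patient type, centre, age, sex, log NT-proBNP and number of HF hospitalisations in the preceding year.

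Allow the NT-proBNP and prior-admission slopes to differ by patient type if needed. Section 3.4.2 requires a recent admission or urgent visit only of HF patients. For LVAD and transplant patients the 12-month count may span time before and after surgery. With six centres and three patient types this is 5 + 2 + 4 = 11 covariate terms, or 15 with the slope interactions, which 398 analysed patients can carry easily.

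State a simple rule for missing baseline values that does not depend on arm. For event-free survival, use a Cox model with the same covariates, stratified by patient type. Keep the unadjusted comparison as a supporting analysis.

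The cost is a change of wording, slightly more analysis work and the discipline of fixing the covariates in advance. No new data are needed, and the model keeps the difference in means on which the trial was sized.

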3.6 Cumulative safety and efficacy information

This is a clinical study which will not involve any drug prescriptions other than those that would be required by established guidelines for the follow up and care of the recruited patients.

3.6.1 Cumulative efficacy information

Not applicable. There is no previous study combining real world data on Heart Failure with data derived from medical devices.

3.7 Conduct

3.7.1 Schedule for study conduct including timelines for key study milestones

The RETENTION clinical study will be conducted according to the following timeline:

- Study subject approvals package: M14
- Ethics approvals for the different clinical units: M20
- First Patient, First Visit (FPFV): M22
- First Patient, Last Visit: M39
- Last Patient, First Visit: M31
- Last Patient, Last Visit: M48 and end of follow ups

3.7.2 Description of recruitment strategy

Candidates for the study are already available from the existing pools of patients available in each of the participating hospitals. The target number of recruited patients for each of the hospitals is shown in Table 1. The recruitment target ratios for the different types of patients will be preserved across the clinical units of each country.

The pool of patients already available will be thoroughly screened based on the last clinical evaluation and the patients considered as potential candidates will be informed about the purpose of the study. Their positive response to the expression of interest will be followed by a new clinical evaluation to assess their current clinical status and obtain their base line for further evaluation.

An informed consent form will be signed prior to the clinical evaluation required for the participation to the study.

3.7.3 Description of the clinical protocol

The RCT will involve the remote monitoring of all patients who will participate in it. This will be enabled through the RETENTION platform, which will be developed to collect data obtained from the smart devices (smartphone, weight scale, pulse oximeter, digital blood pressure monitor, tracker-smartwatch, home sensor for temperature and humidity, home gateway) and the RETENTION mobile application running on the smartphone. All the above will be given to the patients participating in the study by the project. These data will be amalgamated with clinical tests and assessments of the participants of the study as well as real world data obtained from external resources (e.g., environment data from the Copernicus service or other similar).

The following types of data will be collected and analysed.

Data collected upon registration/randomisation:

Demographics:

- Date of birth, age
- Sex (male, female)
- Ethnicity (European, North African, Middle East, Sub-Saharian African, Central Asia, East and South)
- Marital status(single/widow with no family support, single/widow with other family members, living with a partner/spouse)
- Country of residence (Greece, Germany, Italy, Spain)
- Home address (Country, zip code, city, address number)
- Level of education (Up to and including high school, Above high school education, No education, Other)
- Employment status (Working (full or part time), Not currently working, Full-time homemaker, Retired, Student, Other)
- ABO Blood Group (A,B,O,AB)
- Height

Medical cardiovascular History:

- Primary aetiology of heart failure (ischemic: post-ACS, post-MI, post-CABG, post-PCI; non-ischemic: hypertensive, cardiomyopathy, valvular, other; unknown)
- Cardiac transplantation
- Ventricular assist device
- Coronary artery disease (acute coronary syndrome, percutaneous coronary intervention, coronary artery bypass surgery)
- Ventricular tachycardia/Ventricular fibrillation/Resuscitated sudden death
- Brady-arrhythmias/AV block
- Valvular surgery or percutaneous valvular procedures
- Venous thromboembolism / pulmonary embolism
- Carotid Artery Disease
- Stroke / Transient ischemic attack (TIA)
- Atrial Fibrillation
- Diabetes mellitus (type 1 or type 2)
- Arterial hypertension
- Dyslipidaemia
- Peripheral vascular disease
- Permanent Pacemaker (PPM)
- Implantable Cardioverter-Defibrillator (ICD)
- Cardiac Resynchronisation Therapy, with defibrillator (CRT-D) or without defibrillator (CRT-P)
- Aortic Aneurysm
- Heart Transplant
- LVAD Implant
- HF & CV medical therapies (ACEI/ARNI/ARB, BB, MRA, SGLT2i, diuretic, anticoagulant, antiplatelet, statin, amiodarone

Non-cardiovascular history

- Smoker [never, current, past (meaning >6 months)]
- Severe alcohol intake [never, current, past (meaning >6 months)]
- Thyroid disease (if yes, define hyper- or hypo-thyroidism)
- Cancer
- Anaemia
- Chronic Obstructive Pulmonary Disease (COPD)
- Chronic Kidney Disease
- Benign Prostatic hyperplasia
- Other than HF & CV medical therapies
- Recent HF hospitalisation discharge date, or recent urgent ED visit due to HF date
- Number of HF hospitalisations within the last 12 months
- Caregiver data (if caregiver available):
- Sex
- Date of birth, age
- Children (yes/no)
- Living situation (Living alone /Living with the person that cares for only /Living with the person cared for and other family members/ Other)
- Highest level of education (Up to and including high school/ Above high school education/ Other)
- Employment status (Working (full or part time) /Not currently working / Full-time homemaker / Retired /Student or other)
- Caregiver condition (Cardiovascular Disease/ Hypertension/Diabetes mellitus/ High cholesterol)

Data collected at every clinic visit (upon registration and at months 4,8,12 and 18):

- Weight
- Vital signs: Blood pressure, heart rate, Peripheral capillary oxygen saturation, Temperature
- ECG
- Rhythm
- Heart rate
- Conduction delay(LBBB,RBBB, LAH, LPH, incomplete RBBB or LBBB)
- QRS duration
- QTc
- PQ/PR
- Blood tests at months 4,8,12 (Urea, Creatinine, Potassium, Sodium, SGOT, SGPT, LDH, INR, CPK, Troponin, Uric Acid, CRP, White blood cells, Haemoglobin, Platelets and NT-proBNP)
- Blood tests at months 0(registration) and 18(Urea, Creatinine, Potassium, Sodium, SGOT, SGPT, LDH, INR, CPK, Troponin, Uric Acid, CRP, White blood cells, Haemoglobin, Platelets and NT-proBNP, Glucose, Magnesium, Cholesterol, Triglycerides, HDL, LDL, γGT, ALP, Total proteins, Albumin, Total Bilirubin, D-Dimers, Fibrinogen, Calcium, Phosphorus, CRP, Procalcitonin, TSH, FT3, FT4, B12, Fe, Ferritin)
- Depression score PHQ-9
- Kansas City Cardiomyopathy Questionnaire (KCCQ)
- Six-minute walk test
- Cardio-pulmonary exercise testing (upon registration and at month 18)

- VE/VCO2
- VO2max
- RER
- Echocardiography (upon registration and at months 8 and 18)
- Left Ventricular Ejection Fraction (LVEF)
- Left Ventricular End Diastolic Diameter (LVEDD)
- Left Ventricular End Systolic Diameter (LVESD)
- Left Ventricular Posterior Wall (PW) and Interventricular Septum (IVS) Thickness at diastole
- Left Atrium diameter (LA)
- Right Atrium diameter (RA)
- Aortic Root diameter
- Basal right ventricle diameter
- Fractional area change
- Tricuspid Annular Plane Systolic Excursion (TAPSE)
- Right Ventricular Systolic Pressure (RVSP)
- Inferior Vena Cava (IVC)
- Aortic Valve Regurgitation (if yes: trace/mild or moderate or severe)
- Aortic Valve Stenosis (*if yes*: mild or moderate or severe)
- Mitral Valve Regurgitation (*if yes*: trace/mild or moderate or severe)
- Mitral Valve Stenosis (*if yes*: mild or moderate or severe)
- Tricuspid Valve Regurgitation (*if yes*: trace/mild or moderate or severe)
- Tricuspid Valve Stenosis (*if yes*: mild or moderate or severe)
- Interrogation of defibrillator (upon registration and at months 8 and 18)

The following data will be additionally collected for patients with VAD:

- Controller parameters
- Alarms
- RPMs
- Power consumption
- Flow
- Pulsatility index
- Driveline exit site evaluation (photographic evidence) as early signs of infection

Data collected on a daily basis through remote monitoring:

Data collected from smart sensors and devices on a daily basis will be:

- Weight(once per day)
- Blood pressure (morning)- excluding patients with LVAD
- Heart Rate (continuous)
- Peripheral capillary oxygen saturation (morning, evening)
- Sleep: deep and light sleep phases, sleep interruptions.
- Steps, distance, floors climbed, calories consumed

Data collected through self-reporting (via the RETENTION smart phone application):

- Symptoms (once a week or sooner if any worsening is observed by the patient. In patients reporting worsening, they will be asked to specify through the application e.g., swollen feet, shortness of breath, not being able to lie down due to shortness of breath, dizziness, rapid heartbeats).
- Timely adherence to prescribed medication (on the designated time an alarm will be set to remind the patient to take his/her medication timely alarm deactivation will be reported to the platform as proof of adherence).
- Nutrition intake (MNA Score) every 4 months through automatic reminder.
- MOCA and PHQ9 questionnaires ±15 days from each clinic visit
- Heart Failure Caregiver Questionnaire (HF-CQ Version 5.0)(baseline and at month 18)

Data collected through smart environment sensors and the smart watch/phone:

- Patient living space data (temperature, humidity, GPS vicinity)
- Patient living environment data (extreme temperatures and weather conditions, pollutants obtained from Copernicus services)
- Patient outdoor movement

Table 2: Timeframe of patient assessments

Parameter	Registration/Ra ndomisation	Month 4	Month 8	Month 12	Month 18	Daily	Once a week/per need
Age	\checkmark						
Sex	\checkmark						
Ethnicity	\checkmark						
Marital Status	\checkmark						
Country of Residence	√						
Height	\checkmark						
Level of education	1						
Employment status	√						
ABO Blood Group	1						
Cardiovascular history	√						
Non- cardiovascular history	√						
Home Address	\checkmark						
Caregiver data	\checkmark						
Weight	\checkmark					\checkmark	

Parameter	Registration/Ra ndomisation	Month 4	Month 8	Month 12	Month 18	Daily	Once a week/per need
Body Temperature	√					~	
Blood Pressure	1					~	
Heart Rate	\checkmark					✓	
Oxygen Saturation	~					~	
Sleep						✓	
Steps						✓	
Medication Alarm						~	
Symptoms	✓	√	✓	√	✓		✓
Clinical examination	~	√	√	√	√		
MNA Score		\checkmark	\checkmark	\checkmark	\checkmark		
HF-CQ v5	\checkmark				\checkmark		
MOCA	\checkmark						
PHQ9	\checkmark	\checkmark	\checkmark	\checkmark	\checkmark		
КССQ	\checkmark	\checkmark	\checkmark	\checkmark	\checkmark		
ECG	\checkmark	\checkmark	\checkmark	\checkmark	\checkmark		
Blood Tests	\checkmark	\checkmark	\checkmark	\checkmark	\checkmark		
6MWT	\checkmark	\checkmark	\checkmark	\checkmark	\checkmark		
CPET	\checkmark				\checkmark		
ECHO	✓		~		✓		
ICD Interrogation	~		√		√		
VAD Parameters	√	\checkmark	√	\checkmark	√		

